7.5 Sample size

The study will enroll approximately 123 patients, see section 15.2 for sample size calculation.

7.6 Patient replacement

The target recruitment is 123 patients. Randomization will continue until 123 patients are recruited and they receive at least one course of treatment

8. Trial assessments

Quality of life survey	Х	Х
Subsequent AML therapy	Х	Х
Patient diary return and review	Х	

*: a phone call, at minimum, will be performed at 4 months (+/- 1 week) after end of study treatment, for safety assessment

Patient will have to attend visit every 28 days (+/- 3 days), at the start of each cycle, for a duration up to 24 months. Assessments required are provided in Table 4 and Table 5.

When study treatment is stopped (see required conditions in section 8.9), the visits will take place every 3 months until 24-months study duration. Assessments required are provided in Table 6.)

8.2 Inclusion period

The inclusion will take place before treatment beginning in order to obtain patient consent for study participation, verify the inclusion/exclusion criteria and gather the baseline data.

8.3 Registration procedure in IWRS (interactive web response system)

Registration takes place once the patient give his/her consent to participate in the study. Investigator must declare patient inclusion by entering patient data selection in IWRS (see details in Appendix 2) and, after checking all inclusion/exclusion criteria, ask for randomization.

After confirmation of randomization, the system will display the treatment arm allocated and the investigator will receive an e-mail.

A: Low-dose cytarabine

B: Low- dose cytarabine + GRASPA

8.4 Study treatment administration

All patients enrolled, randomized in Arm A or B, will receive successive 28-day courses of subcutaneous low-dose cytarabine 40 mg daily (or 20 mg twice daily) for 10 days per course (from day 1-D1 to day 10-D10), each course occurring every 28 days +/- 3 days, for a duration up to 24 months. SPC for Cytarabine Hospira and Pfizer are attached in Appendix 1 as example. Please refer to country-specific approved Cytarabine SPC for country-specific information.

Following the implementation of Amendment 4, patients randomized in arm B treatment will receive subcutaneous low-dose cytarabine, as described above, and GRASPA 100 IU/kg, given as an intravenous infusion at **Day 11** of each 28-day course.

Required documents such as **Investigator's prescription of GRASPA and Patient's pretransfusional status** (refer to section 9.6) should be sent at ERYTECH Pharma 2 days before the schedule day of GRASPA administration, i.e. Day 9.

In the event the patient cannot receive GRASPA treatment at the planned date (i.e. manufacturing failure) or if GRASPA treatment received on site is not suitable for administration (e.g. transport or cold chain impairment, rupture of bag...), investigator and ERYTECH Pharma will discuss the best treatment approach for the patient:

- Restart manufacture for a new bag of GRASPA (delay GRASPA administration with max one week), if acceptable for the patient.
- Switch the patient to appropriate alternative treatment, at investigator's decision.
 - If the switch occurred before the first GRASPA administration, then the patient will be replaced, as defined in section 7.6.
 - If the switch occurred after at least one administration of GRASPA, treatment for next blocks afterwards will be at investigator's decision (GRASPA will not be resumed if delayed more than 2 weeks; refer to section 8.5.4 "Dosage modifications of GRASPA" and 8.11 "end of study treatment").

8.5 Dosage modification in case of toxicity

8.5.1 General dispositions

- The investigator will carefully monitor treatment toxicity according to standard practice and to the schedule to assessment (section 8.1).
- Supportive therapy and adjustment to concomitant therapies may be prescribed by the investigator according to standard practice.

8.5.2 Transfusion reactions

The clinical symptoms of a transfusion reaction are variable. A few clinical signs of adverse reaction due to transfusion are listed here:

- Feeling of heat, malaise, feeling of burning along the vein
- Chills, fever with or without lumbar and thoracic pain
- Abrupt change in blood pressure, hypertension or hypotension
- Respiratory distress with dyspnea
- Urticarial, rash, localized or extensive edema
- Nausea with or without vomiting
- Hemorrhagic syndrome with bleeding at the site of injection and surgical wound.
- Anaphylactic shock

In case of any transfusion reaction, the first measure to be taken during the administration of GRASPA is to stop the transfusion immediately and then to administer the necessary symptomatic treatments, according to standard of care.

8.5.3 Dosage modifications for cytarabine

- Cytarabine dosage modifications should be applied according to the prescribing information and standard practice. At investigator judgment, if required by patient status, cytarabine dosage increase is acceptable.
- A standard recommendation, in case of toxicity attributed to cytarabine, is to reduce the dosage of cytarabine to 20 mg daily.
- In case of persistent or excessive toxicity attributed to cytarabine, cytarabine may be temporarily or permanently discontinued, as per investigator judgment. In such case, for patients in arm B, GRASPA should be continued as scheduled, every 14 days.

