	 Eligible to receive low-dose cytarabine treatment ECOG performance status ≤ 2 Female patients of childbearing potential and males must agree to use adequate contraception (e.g., hormonal or barrier method of birth control; abstinence) for the duration of study treatment and for 6 months after the last dose of Cytarabine or 3 months after last dose of GRASPA (whichever is the longest). Negative serum pregnancy test at study entry for female subjects of childbearing potential Subscription to social security insurance (if applicable, in accordance with local regulations) Ability to understand, and willingness to sign, a written informed consent document and to comply with scheduled visits, treatment plans, laboratory tests, and other study procedures 						
Main Exclusion Criteria	 Patients with M3 AML of FAB classification (APL, acute promyelocytic leukemia) Patients with AML involving chromosome 16 abnormalities or translocation (8:21) (CBF-AML) Patient with secondary AML subsequent to prior malignant blood disorder such as: Myelodysplastic syndrome diagnosed more than 6 months before study entry Myeloproliferative syndrome 						
	 Prior therapy to AML (standard therapy or investigational agents) Inadequate organ function : Uncontrolled or severe cardiovascular disease including myocardial infarction within 6 months of enrollment, New York Heart Association (NYHA) Class III or IV heart failure, uncontrolled angina, clinically significant pericardial disease, or cardiac amyloidosis. Serum creatinine concentration > 2 x ULN (Upper Limit of Normal) AST or ALT levels > 3.5xULN or 5xULN if related to AML Total bilirubin > 2 x ULN INR > 1.5, unless patient under chronic treatment with anticoagulants (in this case, INR should be within expected ranges for the specific condition) Insulin-dependent or uncontrolled diabetes mellitus Concurrent malignancies other than AML requiring chemotherapy Severe active infection, HIV seropositivity, or known active type B or C viral hepatitis Known or suspected hypersensitivity or intolerance to mannitol Breastfeeding or lactating women 						
Location	EUROPE						

- CONFIDENTIAL -

Study duration	Each patient will be followed for 24 months in the study.								
Study Treatment	In the experimental group, the patients will receive one injection of GRASPA (100 IU/kg) in combination with subcutaneous low-dose cytarabine (same posology as reference group hereafter), every 28 days.								

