Date of Initiation	Q1 2013						
Planned Date of	Q1 2018 (last patient last visit)						
completion	Recruitment duration = 36 months + 24 months follow-up						

2. Trial diagram

Figure 1: Study diagram

Patients included in the study will undergo successive courses of study treatment, for a duration up to 24 months. A course is defined as 28 days, with Day 1 being the first day the patient receive low-dose cytarabine (Figure 1: Study diagram).

Patient will have to attend a visit once a month, at the start of each course.

When study treatment is stopped (see required conditions in section 8.9), the visits will take place every 3 months until the 24 months study duration has been reached.

Refer also to section 8 for study treatment and assessments.

3. Introduction and rationale

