5.1 Potential benefit for elderly patients with first AML diagnosis

In elderly AML patients with standard cytogenetic risk, treatment with intensive chemotherapy results in median overall survival of up to 12 months, whereas in the adverse cytogenetic category median survival is only 2-3 months (Lagadinou, 2010). The median age at presentation for patients with AML is about 65 years and in this age group, AML is associated with a poor prognosis. Therefore, AML in the elderly represents a major unmet medical need.

Asparaginase has been used in some treatment protocols for AML in children. Capizzi (1988) has reported a significant benefit of Asparaginase in AML. However, its use remains hampered due to its toxicity. The use of L-asparaginase has a potential interest in AML, in light of the fact that AML blasts display a low level of ASNS (see section 3.2).

GRASPA has been proposed as a new approach to maintain the activity of L-asparaginase while improving its safety profile. Recent experience of GRASPA in ALL with an elderly population >55 years, demonstrated a

tolerable safety profile. This study showed that GRASPA favorable safety profile of both doses 100 and 150 IU/Kg (GRASPALL 2007-04). A recent PK/PD re-analysis of all completed studies with GRASPA demonstrated that age has no impact on the PK of different dosing levels; and therefore, a dosing schedule of 150 IU/Kg every 2 weeks is proposed as a standard dose for all age groups.

The objective of the development of GRASPA in AML is evaluate the overall survival benefit and the both progression free survival and event free survival and patient quality of life, as well as assess the impact on ASNS profile of myeloblasts as an exploratory objective.

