8.5.4 Dosage modifications for GRASPA

- If patient cannot receive GRASPA, for another reason than an adverse event, treatment may be postponed no later than one week after the initial scheduled day. A minimum two weeks interval between GRASPA infusions must be insured.
- In case of allergic reaction during administration, stop the administration immediately and then to administer the necessary symptomatic treatments, according to standard of care. Further administration of GRASPA will be at investigator judgment, considering possibility of premedication anticipated for such case.
- In case of any Grade 3 or 4 adverse event related to GRASPA occurring in two successive infusions, GRASPA should be discontinued.
- In the event of bilirubin levels >3 times upper limit of normal or transaminase levels >10 times upper limit of normal, treatment with GRASPA should be discontinued.

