9.2 Posology

GRASPA is a ready to use suspension designed to be fully injected.

The dose of GRASPA is 100 IU/kg. In this study protocol, patients will receive one infusion of GRASPA on Day 11 of 28-day course of chemotherapy (see section 10.1).

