17.1 Trial duration

Trial assessment will last 24 months for each patient.

Patient treatment will consist in successive 28-days blocks of low intensive chemotherapy (number of blocks depends on treatment response).

Investigational product is given/ provided during the whole period the patient is under low intensive chemotherapy.

Recruitment period planed: 3 years

Expected start date: Q1 2013

Expected completion date: Q1 2018

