3. STUDY DESIGN

3.1. Synopsis of Study Design

This is a multicentre, open label, randomized 1:2 (control versus GRASPA), controlled phase IIb trial in Europe, evaluating efficacy and tolerability of GRASPA. The trial follows the scheme below:

In both treatment and control arms, patients will be treated with subcutaneous LDAC as 40 mg daily (either one single dose of 40 mg or 20 mg twice daily according to local practice) for 10 consecutive days per course, each course occurring every 28 days \pm 3 days, for a duration up to 24 months. Each period of 28 days constitutes a cycle of chemotherapy. The dosage could be adjusted to 20 mg once daily in case of toxicities; a higher dose is also acceptable if required by the patient's status, at the investigator's decision.

In the experimental group, the patients will receive subcutaneous LDAC, as described above, and GRASPA (100 U/kg) given as an intravenous infusion at Day 11 of each 28 day course.

Patients will be required to attend a visit once a month, as the course begins.

When study treatment is stopped (main expected reasons are limiting toxicity, PD, or no evidence of treatment benefit), the visits will take place every 3 months until 24-months study duration has been reached.

An Independent Data Monitoring Committee (IDMC) was set-up for regular data reviews for safety: they reviewed the tolerance of GRASPA when 30 patients had been enrolled, to evaluate limiting toxicities defined as one of the following:

- grade 3 or 4 pancreatic toxicity
- grade 3 or 4 hepatic toxicity, allergic reaction, or coagulation event

- other non-hematologic grade 4 toxicity or requiring treatment change at investigator's decision

Specific attention is paid on type II diabetic patients treated with oral hypoglycemic agents for their diabetes, randomized to LDC + GRASPA.

The IDMC also reviewed safety and tolerance of GRASPA when 60 patients had been enrolled, at the end of recruitment and when 60 PFS events had been observed.

Additional information is provided in the IDMC Charter and the minutes of the IDMC meetings.

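### Protocol 8.5.3 continues arm B GRASPA every 14 days when cytarabine is held or stopped, but the study schedule is one infusion per 28-day course; followed literally, the rule doubles the GRASPA dose rate

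*Protocol*

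**What the plan says.** The exception is in Protocol 8.5.3. If toxicity attributed to cytarabine persists or is excessive, the investigator may interrupt cytarabine or stop it for good. The section then states: "In such case, for patients in arm B, GRASPA should be continued as scheduled, every 14 days".

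The places that set the regimen agree with one another and not with that sentence:

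- **Protocol synopsis, Study Treatment:** one 100 IU/kg injection "in combination with subcutaneous low-dose cytarabine (same posology as reference group hereafter), every 28 days".
- **Protocol Table 4:** GRASPA is marked at Day 11 only, with one irregular antibody screening test (IAST) per course, at Day 9.
- **Protocol 8.4:** 100 IU/kg on Day 11 of each 28-day course, with courses starting every 28 days +/- 3 days.
- **Protocol 9.2:** "patients will receive one infusion of GRASPA on Day 11 of 28-day course of chemotherapy".
- **SAP 3.1:** "GRASPA (100 U/kg) given as an intravenous infusion at Day 11 of each 28 day course".

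Two other statements bear on the point. Protocol 8.5.4 sets a floor on spacing: "A minimum two weeks interval between GRASPA infusions must be insured". Protocol section 2 ties the course calendar to cytarabine: "A course is defined as 28 days, with Day 1 being the first day the patient receive low-dose cytarabine".

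**The concern.** The 8.5.3 sentence points to the existing schedule and, in the same breath, names an interval that the schedule does not contain. Both cannot be followed. It is an operative dosing instruction, not background text, and it applies to patients aged 65 to 85 who have just had cytarabine held or stopped for toxicity. A site that takes the stated interval at face value gives twice the planned rate of the investigational product.

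There is a related gap. Day 1 is defined by the first cytarabine dose of the course. Once cytarabine is not being given, Day 11 has no stated reference date. A site that correctly rejects the 14-day interval still has no written rule for dating the next infusion.

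The conflict also touches reporting. A site cannot comply with both 8.5.3 and 9.2, so the protocol does not settle which practice is a deviation. The planned tables on GRASPA dose intensity and compliance (SAP 8.1, Tables 14.1.6.2.1 and 14.1.6.2.2) need a planned dose, and for these patients it depends on which sentence is used.

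**Working it through.** **Inputs**

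- Dose per infusion: 100 IU/kg (Protocol 9.2).
- Study interval: 28 days (synopsis, Table 4, 8.4, 9.2, SAP 3.1).
- Interval stated in 8.5.3: 14 days.
- Minimum interval in 8.5.4: two weeks, or 14 days.
- Suspension volume of a 100 IU/kg infusion: 1.8 mL/kg (Protocol 5.2.2).

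**Step 1: what interval does the schedule imply?** Day 11 of one course to Day 11 of the next is one course length, 28 days. With the +/- 3 day window it is 28 - 3 = 25 to 28 + 3 = 31 days. The 14 days in 8.5.3 cannot be reproduced from the schedule.

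**Step 2: exposure per 28 days.** Infusions = 28 / interval. Dose = infusions x 100 IU/kg. Volume = infusions x 1.8 mL/kg.

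| | Study schedule | 8.5.3 read literally |
|---|---|---|
| Infusions | 28/28 = 1 | 28/14 = 2 |
| Dose | 1 x 100 = 100 IU/kg | 2 x 100 = 200 IU/kg |
| Dose rate | 100/28 = 3.57 IU/kg/day | 100/14 = 7.14 IU/kg/day |
| Volume | 1 x 1.8 = 1.8 mL/kg | 2 x 1.8 = 3.6 mL/kg |

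The ratio is 28/14 = 2.

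**Step 3: does 8.5.4 block the shorter interval?** The requirement is an interval of at least 14 days. Since 14 >= 14, it does not.

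**Step 4: does the corrected rule fit 8.5.4?** The shortest interval under the corrected rule is 25 days. If the earlier infusion was postponed by the full week that 8.5.4 allows, the interval is 25 - 7 = 18 days, which still exceeds 14.

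**The case against.** The strongest reply is that few sites would double the dose. The sentence itself refers to the schedule, and each place that sets the regimen gives one infusion per 28 days. A second infusion also could not simply happen at the site. Each bag is made on an individual prescription with a stated administration date. It needs an IAST less than 72 hours old (9.6), while the calendar has only one per course. The prescription form in Appendix 5 also has a box for dated and signed sponsor confirmation. All of this stands, and it lowers the urgency. It does not remove the error: the form pre-prints the dose but leaves the date open, and none of these steps tells the site or the sponsor which interval is right.

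A reader might infer several stronger things that the documents do not support:

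- **That GRASPA should cease when cytarabine is permanently stopped.** Protocol 17.1 says "Investigational product is given/ provided during the whole period the patient is under low intensive chemotherapy". That is a general statement about duration, not a stopping rule. Section 8.5.3 expressly continues GRASPA in this case, and the list of reasons to end treatment in 8.11 does not include stopping cytarabine alone. The real ambiguity is 1 versus 2 infusions per 28 days.
- **That a two-weekly schedule was intended.** Section 5.1 remarks that "a dosing schedule of 150 IU/Kg every 2 weeks is proposed as a standard dose for all age groups". That is background at a different dose, and no treatment section adopts it. Whether it would mislead a site is conjecture.
- **That the doubled volume nears a full transfusion.** By raw volume, 3.6/4.6 = 78% of the ordinary red-cell unit in 5.2.2, but the two suspensions differ in concentration. By haemoglobin the comparison is 3.6 x 0.13 = 0.468 against 4.6 x 0.18 = 0.828 g/kg, or 57%. By packed cells it is 3.6 x 0.50 = 1.80 against 4.6 x 0.60 = 2.76 mL/kg, or 65%. Even doubled, it stays below one ordinary unit.

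**Conclusion.** The point holds as an internal inconsistency: the interval in 8.5.3 is wrong as written. Followed literally, it doubles GRASPA from 1 to 2 infusions, 100 to 200 IU/kg and 1.8 to 3.6 mL/kg per 28 days, for arm B patients with cytarabine held or stopped. The factor of 2 assumes that each infusion stays at 100 IU/kg and that the site acts on the stated interval.

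The limits are clear. The documents do not show that 200 IU/kg per 28 days is unsafe. They do not say how many patients have cytarabine interrupted, so the number affected is unknown. A reader might infer that the primary result is compromised. The documents do not support that: the intention-to-treat set is defined by randomization, and neither that set nor the planned overall survival analysis changes. Given the practical safeguards, this should be fixed, but it does not threaten the trial's conclusions.

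**What to change.** In Protocol 8.5.3, replace the 14-day interval with: *once every 28 days (+/- 3 days), on Day 11 of the course, with Day 1 counted as the date the cytarabine course would have started*. This corrects the interval and supplies the missing reference date.

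Aligning 17.1, so that it plainly allows GRASPA to continue after cytarabine is stopped, is optional.

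The cost is a clarification letter or a short amendment changing one phrase. It needs no extra patients, visits or procedures.

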8.5.4 Dosage modifications for GRASPA

- If patient cannot receive GRASPA, for another reason than an adverse event, treatment may be postponed no later than one week after the initial scheduled day. A minimum two weeks interval between GRASPA infusions must be insured.
- In case of allergic reaction during administration, stop the administration immediately and then to administer the necessary symptomatic treatments, according to standard of care. Further administration of GRASPA will be at investigator judgment, considering possibility of premedication anticipated for such case.
- In case of any Grade 3 or 4 adverse event related to GRASPA occurring in two successive infusions, GRASPA should be discontinued.
- In the event of bilirubin levels >3 times upper limit of normal or transaminase levels >10 times upper limit of normal, treatment with GRASPA should be discontinued.

8.6 AML assessment

Initial bone marrow aspirate/biopsy must be available within four weeks prior randomization, for baseline blast count.

AML assessment will be performed for each course, in order to allow AML disease evaluation and response to treatment based on adapted Dohner criteria (see Table 3 for Response criteria definitions)

8.7 Laboratory assessments

8.7.1 Biological parameters

Biological assessment will be performed according to the investigational center procedure at inclusion, and then, at D1, D5, D9, D13, D18, D23 and D27 of each course of chemotherapy (± 2 days).

Following measurement should be performed:

- Hematology: Complete Blood Count (CBC), platelets;
- Coagulation parameters: Prothrombin Time (PT), activated Partial Thromboplastin Time (aPTT), fibrinogen, antithrombin III, INR;
- Chemistry: bicarbonate, sodium, potassium, calcium, creatinine, creatinine clearance (calculated by Cockroft & Gault formula), albumin, bilirubin, alanine amino transferase (ALT), aspartate amino transferase (AST), alkaline phosphatase, gamma glutamyl transpeptidase (GGT), lactate dehydrogenase, glucose, cholesterol, triglyceride, lipase, amylase;
- Serologic test for HIV, B and C hepatitis will be made at inclusion only, if needed.
- Serum pregnancy test for women with childbearing potential at inclusion and end of treatment.

Assessed and signed anonymized lab reports must be sent to sponsor/representatives as soon as possible after receiving the results for protocol required tests as well as for any testing performed for management of AEs.

